4.2 Endpoints

The primary efficacy endpoint for the study is:

- Percentage change in PASI score from baseline at Week 16.

The secondary efficacy endpoints for the study are:

- Percentage change in PASI score from baseline at Weeks 4, 8 and 12.
- Absolute change from baseline in PASI score at Weeks 4, 8, 12 and 16.
- Achievement of PASI-50 at Weeks 4, 8, 12 and 16.
- Time to first achievement of PASI-50.
- Achievement of PASI-75, PASI-90 and PASI-100 at Week 16.
- Achievement of PGA of 0 or 1 with a ≥ 2 -point improvement from baseline at Week 16.
- Achievement of PGA of 0 at Week 16.
- Percentage change from baseline in PGA*BSA at Weeks 4, 8, 12, and 16.
- Absolute change from baseline in PGA*BSA at Weeks 4, 8, 12, and 16.
- Percentage change from baseline in LSS at Weeks 4, 8, 12, and 16.
- Absolute change from baseline in LSS at Weeks 4, 8, 12, and 16.
- Percentage change from baseline in DLQI score at Weeks 4, 8, 12, and 16.
- Absolute change from baseline in DLQI score at Weeks 4, 8, 12, and 16.
- Percentage change from baseline in mNAPSI total score at Weeks 4, 8, 12, and 16.
- Absolute change from baseline in mNAPSI total score at Weeks 4, 8, 12, and 16.
- Cumulative incidence of partial relapse at Weeks 20, 24, 28, and 40.
- Cumulative incidence of complete relapse at Weeks 20, 24, 28, and 40.
- Cumulative incidence of rebound at Weeks 20, 24, 28, and 40.

Exploratory efficacy endpoints are:

- Achievement of PASI-50, PASI-75, PASI-90, and PASI-100 at Weeks 4, 8, and 12.
- Achievement of PGA of 0 or 1 with a ≥ 2 -point improvement at Weeks 4, 8, and 12.
- Achievement of PGA of 0 at Weeks 4, 8, and 12.
- Achievement of PGA of 0 or 1 at Weeks 4, 8, 12, and 16.
- Percentage change from baseline in BSA at Weeks 4, 8, 12, and 16.
- Absolute change from baseline in BSA at Weeks 4, 8, 12, and 16.
- Achievement of BSA<3% and BSA-75 at Weeks 4, 8, 12, and 16.
- Absolute change from baseline in PSI quality of life total and itch scores at Weeks 12 and 16.
- Percentage change from baseline in PSI quality of life total and itch scores at Weeks 12 and 16.
- Absolute change from baseline in Pain and Fatigue scores at Weeks 4, 8, 12, and 16.
- Percentage change from baseline in Pain and Fatigue scores at Weeks 4, 8, 12, and 16.
- Absolute change from baseline in fasting blood glucose and fasting lipid panel at Weeks 8 and 16.
- Mean duration of remission in participants who achieve PASI-100.

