5.3.3.2 Psoriasis Area and Severity Index

PASI score will be calculated within the eCOA system and taken directly from the supplied data. Further information on the scoring of the PASI is provided in [Section 16](#).

PASI-50, PASI-75, PASI-90 and PASI-100 responses are defined respectively by at least a 50%, 75%, 90% and 100% reduction from Baseline in the PASI score.

Response at Week 16 is defined as achieving PASI-50 or greater at the Week 16 visit.

Partial relapse is defined, after the Week 16 visit, as loss of PASI-50 response after cessation of study treatment, or the participant begins a new treatment for psoriasis.

Relapse is defined, after the week 16 visit, as an increase in PASI score to the baseline value or greater, or the participant begins a new treatment for psoriasis.

Rebound is defined as an increase in PASI score to 125% of baseline value or above, or onset of new pustular/erythrodermic psoriasis, within 3 months of cessation of study treatment.

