7.7 Visit Windows

All data will be reported according to nominal visits, except for subjects who complete the follow-up Week 20 assessments due to withdrawing from the study before the Week 16 visit. For example, if a Week 2 visit occurred on Day 16 instead of the nominally expected Day 14 it will be reported and included in the summary statistics/statistical analyses for Week 2.

Subjects who withdraw prematurely from the study should complete the assessments required for the follow-up visit (Week 20). However, this data will only be included in tables and figures which are produced **by visit** for subjects who completed the 16-week treatment period and provided Week 16 data prior to the Week 20/follow-up data being collected. Tables and figures which do not show summaries by visit and all listings will include all collected Week 20/follow-up data regardless of whether the subject completed the 16-week treatment period.

Scheduled visits which occur outside the protocol-specified visit window (e.g. if the Week 2 visit occurred on Day 19 outside of the Day 12-18 window), this will be noted as a protocol deviation but data collected will still be included in all summary and analysis tables.

Unscheduled visits will not be included in summary or analysis tables, unless they are baseline measurements or provide data towards a safety endpoint which looks at worst-case post-baseline.

8 Summary of Study Data

All continuous variables will be summarized using the following descriptive statistics: n (non-missing sample size), mean, SD, median, maximum and minimum. The frequency and percentages (based on the non-missing sample size) of observed levels will be reported for all categorical measures.

In general, all data will be listed, sorted by randomized treatment (Placebo, EDP1815), cohort (1, 2, 3), site number and participant number. Relevant listings will include whether the assessment was performed and the date, study day/visit and time of the assessment as applicable.

Unless otherwise specified below, all summary tables will be structured with a column for each treatment. Where appropriate, columns combining all placebo participants, all EDP1815 participants and an overall total column may also be presented.

For summaries of study disposition, demographic and baseline data and study treatment compliance, columns will be ordered and labelled as follows:

- Placebo 1 capsule
- EDP1815 1 capsule
- Placebo 4 capsules
- EDP1815 4 capsules

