9.5.6 Partial Relapse, Relapse and Rebound

The following endpoints will be summarised by treatment group and visit in the

- Week 16 responders population:
 - Cumulative incidence of partial relapse at Weeks 20, 24, 28, and 40
 - Cumulative incidence of complete relapse at Weeks 20, 24, 28, and 40
- mITT population:
 - Cumulative incidence of rebound at Weeks 20, 24, 28, and 40

These summary tables will include the number of participants meeting the criteria for the endpoint, and the number of participants 'at risk' of meeting the criteria (the denominator for the cumulative incidence i.e. excluding any participants with a missing status for that endpoint).

For each endpoint, the cumulative incidences for each treatment group will be plotted against time (Week 20 to Week 40) as bars (with an 'error bar' for the corresponding 95% CI).

No inferential analysis of relapse or rebound will be carried out.

Table 6 Intercurrent Event Strategies for Partial Relapse, Relapse and Rebound Endpoints

Endpoint	Intercurrent event	Strategy to account for intercurrent event
Partial Relapse and (Complete) Relapse	Starting a new psoriasis treatment	Composite Starting a new psoriasis treatment is part of the endpoint definition

Endpoint	Intercurrent event	Strategy to account for intercurrent event
Rebound	Starting a new psoriasis treatment	
While in the period following cessation of study treatment, without taking a new psoriasis treatment (analogous to While on treatment)
 
Rebound status will be considered missing from 4 days after the day a new psoriasis treatment is started, onwards, and will not be counted in the denominator during calculation of cumulative incidences

Note that, according to the study design, starting a new psoriasis treatment (synonymous with study treatment failure) should result in a subject completing a PASI questionnaire at an unscheduled Follow-up (Part A)/Early Withdrawal (Part B) visit within 72 hours and then being withdrawn from the study. The above strategies for dealing with the intercurrent event of starting a new psoriasis treatment are included to cover the possibility of a protocol deviation occurring whereby a participant is not withdrawn from the study within 72 hours following the start of a new psoriasis treatment, and to clarify the estimand for rebound.

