Once a participant has met the criteria for partial relapse, relapse or rebound (see [Section 5.3.3.2](#)) they will be counted as having met those criteria at the current (if a PASI criterion at Week 20 or later) or next, and all subsequent, scheduled visits where these endpoints are analysed (Week 20, 24, 28, and 40).

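### SAP 7.7 and 9.5.6 conflict on whether the PASI taken when new psoriasis therapy starts counts towards rebound, and within 9.5.6 Table 6 conflicts with the carry-forward rule

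*SAP*

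**What the plan says.** **General rule.** SAP 7.7 ends with: "Unscheduled visits will not be included in summary or analysis tables, unless they are baseline measurements or provide data towards a safety endpoint". The safety exception is for worst-case post-baseline summaries. An earlier paragraph of 7.7 deals with the Week 20 follow-up assessments of participants who withdraw prematurely. Those data enter by-visit tables and figures only if the participant finished 16 weeks of treatment and already had Week 16 data.

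**Endpoint.** SAP 4.2 lists "Cumulative incidence of rebound at Weeks 20, 24, 28, and 40" among the secondary efficacy endpoints. SAP 5.3.3.2 says "Rebound is defined as an increase in PASI score to 125% of baseline value or above", with new pustular or erythrodermic disease as an alternative, within 3 months of stopping study treatment. Starting new therapy is not part of the rebound definition. It is part of the definitions of relapse and partial relapse.

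**Endpoint-specific rules.** SAP 9.5.6 summarises rebound by visit in the mITT population. It says that starting a new psoriasis treatment should lead to the participant "completing a PASI questionnaire at an unscheduled Follow-up (Part A)/Early Withdrawal (Part B) visit within 72 hours and then being withdrawn from the study". Table 6 adds: "Rebound status will be considered missing from 4 days after the day a new psoriasis treatment is started, onwards", and takes the participant out of the denominator. The closing rule of 9.5.6 says that once participants have met the criteria "they will be counted as having met those criteria at the current" or next scheduled visit, and at every later one.

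**The concern.** A participant whose psoriasis flares after stopping study drug may well start other therapy between scheduled visits. The PASI taken at that moment can be the only record of a PASI-based rebound. If 7.7 is programmed as written, that score does not reach the rebound table. Table 6 then makes later status missing and shrinks the denominator.

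A loss of this kind would be selective, because it falls on participants who worsened enough to need treatment. Evaluating relapse and rebound after cessation is a stated secondary objective, and the incidence of rebound is a stated purpose of Part B. Relapse and partial relapse are not exposed in this way, because the new therapy is itself the event.

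**Working it through.** The plan states no rebound rate and no calculation for this endpoint, so there is no figure to reproduce. The check compares the texts and then gives an illustration.

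**1. Does either 7.7 exception apply?** The score is post-baseline, and rebound is listed as an efficacy endpoint (SAP 4.2). Neither exception applies.

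**2. Does 9.5.6 leave the score usable?** The PASI is due within 72 hours, which is 3 days. Status turns missing from 4 days after the new therapy starts. Since 3 < 4, a PASI taken on time falls before the cut-off and is usable under 9.5.6.

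**3. Who is affected?** For a participant who starts new therapy and meets the PASI criterion at the resulting visit:

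| Situation | SAP 7.7 | SAP 9.5.6 |
|---|---|---|
| Stopped before Week 16; Part A follow-up visit | Expressly kept out of by-visit tables | In the mITT population; score usable before the cut-off |
| Completed treatment with Week 16 data; Part A follow-up visit | Retained | Score usable before the cut-off |
| Part B; Early Withdrawal visit | Not named; excluded if it counts as unscheduled | Score usable before the cut-off |

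The conflict is explicit in the first row, absent in the second, and a matter of interpretation in the third. Protocol Table 6-2 gives the Early Withdrawal visit its own column, but with no day or window. Protocol 4.2.2 uses the word unscheduled only for the Part A follow-up visit. The wording in SAP 9.5.6 can be read as applying it to both.

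**4. Can a later visit recover the event?** Not by design. The participant should then be withdrawn (SAP 9.5.6), and participants counted as treatment failures do not attend Visits 12 and 13 (Protocol Table 6-2, footnote b).

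**5. Table 6 against the closing rule of 9.5.6.** Take a participant who met the rebound criterion and started new therapy, with the next scheduled visit more than 4 days later. Table 6 read alone makes the status missing at that visit and afterwards, and removes the participant from the denominator. The closing rule counts the participant as a rebound at the same visits. Read alone, Table 6 could even make a cumulative incidence fall from one visit to the next. This conflict remains however 7.7 is resolved.

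**6. Illustration (assumed counts).** Let N be the group size, s the rebounds seen at scheduled visits, and u the rebounds seen only at the treatment-start visit. All other participants are assumed to have known status, and the s rebounds are assumed to stay counted.

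- Counted and carried forward: (s + u)/N
- Dropped, and out of the denominator: s/(N − u)

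Group sizes are the planned numbers in SAP Section 6: 50 per active dose and 75 for pooled placebo. With s = 2:

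| N | u | Counted | Dropped |
|---|---|---|---|
| 50 | 1 | 3/50 = 6.0% | 2/49 = 4.1% |
| 50 | 2 | 4/50 = 8.0% | 2/48 = 4.2% |
| 50 | 4 | 6/50 = 12.0% | 2/46 = 4.3% |
| 75 | 1 | 3/75 = 4.0% | 2/74 = 2.7% |
| 75 | 2 | 4/75 = 5.3% | 2/73 = 2.7% |
| 75 | 4 | 6/75 = 8.0% | 2/71 = 2.8% |

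If u = 0, both formulas give s/N and the readings agree.

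**The case against.** A reader might infer from the last sentence of 7.7 that rebounds leading to new therapy are simply lost. The documents do not support that, for four reasons.

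- SAP 7.7 itself keeps the follow-up data of treatment completers who have Week 16 data.
- Table 6 does not exclude the 72-hour PASI. Its 4-day limit leaves that score usable.
- The closing rule of 9.5.6 assigns a met criterion to the next scheduled visit where necessary. That anticipates events found between visits and points towards counting them.
- The Part B Early Withdrawal visit is a defined visit in Protocol Table 6-2, so 7.7 may not reach it.

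It can also be said that an endpoint-specific section should override a general one, that the pustular or erythrodermic limb needs no PASI, and that 9.5.6 plans no inferential analysis of rebound.

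Most of this stands, and it limits the point. It shows what the authors probably intended. It does not settle the conflict: 7.7 is worded as a flat exclusion, no text gives 9.5.6 precedence, and the list of changes in SAP Section 13 does not address it. The explicit bar on by-visit use of follow-up data from early stoppers is untouched by these arguments, and so is the disagreement between Table 6 and the closing rule. A descriptive incidence can still be biased.

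**Conclusion.** The SAP gives conflicting instructions on whether the treatment-start PASI counts towards rebound, and on whether a rebound already met stays counted after new therapy starts. Under the literal reading of 7.7, PASI-based rebound incidence is biased downward. The exposure is clearest for participants who stopped before Week 16. In Part B it depends on whether the Early Withdrawal visit is unscheduled. Treatment completers with Week 16 data who have the Part A follow-up visit are not exposed to the 7.7 exclusion.

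The size cannot be derived from the documents. The 8.0% against 4.2% example rests on assumed counts and on the adverse reading being applied to every event seen only at treatment start. Some rebounds may go unmeasured whichever rule is used, because the protocol asks for the 72-hour visit only where relevant and possible. Relapse, partial relapse and the duration endpoints need no change when new therapy starts, since it already serves as the event or the end date (SAP 5.3.3.2, 5.3.3.4 and Table 6). The point should be settled before programming.

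**What to change.** 1. In SAP 7.7, add an exception: PASI from the Follow-up or Early Withdrawal visit, including for participants who stopped treatment before Week 16, is used for the rebound endpoint in 9.5.6.
2. In SAP Table 6, state that a participant who met rebound before the 4-day cut-off stays in the numerator and denominator at all later visits, in line with the closing rule of 9.5.6. Status is set to missing only for participants who had not met it by then.

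The cost is two sentences in the SAP. No new data are needed.

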8.1 Study Disposition

Completion/withdrawal from the study and completion/discontinuation from treatment, together with reasons for withdrawal from the study or discontinuation from treatment will be listed and the following will also be tabulated:

- Number and percentage of participants who completed the study (Part A for the primary analysis and Part B for the final analysis)
- Number and percentage of participants withdrawn from the study and the reported reason for withdrawal (Part A for the primary analysis and Part B for the final analysis)
- For the interim analyses, the number and percentage of participants still ongoing in the study will also be presented
- Number and percentage of participants who completed the 16-week treatment period (primary analysis)
- Number and percentage of participants who discontinued treatment early and reason for discontinuation (primary analysis)

For participants who fail screening, the reasons for screen failure including details on which inclusion/ exclusion criteria were not met will be summarised and listed.

The number and percentage of participants enrolled within each country and within each site will be summarised.

For the enrolled population, the number and percentage of participants in each analysis population will be presented. Inclusion/exclusion in each study population will also be listed, together with reasons for exclusion.

The number and percentage of participants with data available for each scheduled visit will be summarised.

Missed visits and assessments due to COVID-19 will also be summarised and listed.

8.2 Protocol Deviations

The number and percentage of participants in the mITT population with at least one protocol deviation with a potential impact on efficacy in each category specified in [Table 2](#) will be summarised.

All protocol deviations will also be listed.

8.3 Demographic and Baseline Variables

Demography data of age, sex, race, ethnicity will be summarised together with height, weight and BMI at screening.

Baseline disease characteristics of time (years) since diagnosis and any current psoriasis treatment at the time of the Screening visit will be summarised.

8.4 Medical History

Medical history and concurrent illnesses will be captured and coded using the v23.0 of the Medical Dictionary for Regulatory Activities (MedDRA®).

Concurrent illnesses and medical conditions will be classified as 'current' if the end date is on or after the date of first dose of study drug, or the condition has been marked as ongoing. Otherwise they will be classified as 'past'.

Past and current medical history will be summarised separately by System Organ Class (SOC) and Preferred Term (PT). Summary tables will contain the number and percentage of patients. A patient who has multiple conditions in the same SOC or with the same PT will be counted only once in the patient counts. Medical history summaries will be sorted by the internationally agreed SOC order ([Table 9](#)) and decreasing frequency of PT within SOC in the Total column.

All medical history data will be listed.

8.5 Prior and Concomitant Medications

Medications will be coded according to the World Health Organization Drug Dictionary (WHODD) Version dated 01Mar2020. Medical procedures will not be coded.

Concomitant medications are defined as any medications taken during the treatment period or follow-up period after treatment. This includes any medications started before the first dose and ongoing after the first dose. Prior medications are defined as any medication taken before or during the screening period which were stopped before the first dose of study medication.

Missing and partial start and stop dates will be imputed using the rules specified in [Section 7.3.1](#) before classifying therapies as prior or concomitant. If the classification is still ambiguous after missing and partial dates have been imputed, then the medication will be considered concomitant.

Medications will be summarised by WHODD Anatomical Main Group (Level 1), Therapeutic Subgroup (Level 2) and preferred term. The summaries will report incidence within each relevant level so that a participant taking multiple medications coded to the same relevant Level 1, Level 2 or preferred term would only be counted once within the incidence count for that level or term.

In the primary analysis separate summaries will be produced for each of the following:

- Prior medications
- All Concomitant medications
- Concomitant medications started pre-treatment
- Concomitant medications during the treatment period (including any which started pre-treatment)
- Concomitant medications started during the follow-up period

All prior and concomitant medications will be listed.

In the final analysis concomitant medications started during Phase B and medications from Phase A which changed during Phase B will be listed.

8.6 Treatment Compliance

Treatment compliance will be summarised for each 8-week treatment period and for the whole 16-week treatment period.

Summary statistics (n, mean, SD, median and range) will be produced together with the number and percentage of participants within each of the categories defined in [Section 5.3.2.2](#). Percentages will use the number of participants who started the relevant treatment period as the denominator.

Data from the dosing log and the calculated treatment compliance in each treatment period will also be listed.

9 Efficacy Analyses

In addition to the inferential analyses described below, descriptive statistics will be provided to summarize all efficacy endpoints by treatment group.

For categorical variables, summary tabulations of frequency and percentage of participants within each category will be presented.

For continuous variables and duration endpoints, the number of participants, mean, median, standard deviation (SD), minimum, and maximum values will be presented.

For time to event endpoints, the number of participants with the event, the number of participants censored will be presented together with Kaplan-Meier estimates of time to 25% and 50% (median) of participants with event. Kaplan-Meier curves of time to event will also be presented.

9.1 Pooling of Placebo Cohorts

The assumption that the 3 cohorts of placebo participants can be pooled into a single placebo group to be used as a control for all active doses will be examined using mean (\pm SD) and box plots of percent change in PASI score against time. In addition, a mixed model for repeated measures (MMRM) model will be used to compare the 3 cohorts of placebo participants. The model will include parameters for cohort, visit and baseline PASI score together with cohort*visit and baseline PASI score*visit interactions. LS mean (95% CI) estimates for each placebo cohort will be plotted by visit.

A decision will be made by the Evelo study team, based on examination of the above figures and model, on whether the pooling strategy is appropriate.

If any placebo cohort is considered too different from the other placebo cohorts then no pooling will be used. The pooling of 2 cohorts only will not be considered.

If the pooling strategy is considered appropriate, then the placebo cohorts will be pooled into a single 'all placebo' group for all efficacy analyses and will be used as a common control group for each active EDP1815 treatment group.

If the assumption of similarity across the placebo groups is found to be unreasonable, each placebo dose will be included in the model as a separate dose level and pairwise comparisons between each active EDP1815 dose and placebo will be performed using only the matching placebo dose data from the same cohort.

All efficacy data will be listed, including both individual item scores and calculated questionnaire summary scores.

